Individually Tailored Lighting System to Improve Sleep in Older Adults

NCT01855126

November 5, 2018

Statistical Analysis

We will determine whether the lighting treatments significantly affect the primary outcomes, the nighttime sleep measures (minutes of sleep, sleep onset latency, sleep efficiency, and circadian rhythmicity from actigraphy data; PSQI score; MALSQ score) and safety measures, as well as the secondary endpoints. The primary analytic strategy for the efficacy analyses will employ linear mixed models with measures from the actigraph data (a fourteen-day baseline, plus two seven-day intervention data collection periods for each treatment condition) or one of the survey sleep measures (two observations per treatment condition) as the dependent variable, a random effect for study participant, and a fixed effect for treatment (i.e. a dummy variable for the experimental condition, with the control condition as the reference category). These analyses allow for different numbers of observations for different participants. As part of data cleaning prior to analysis, actigraph data recorded while the monitor is not worn will be identified and removed from the analyses. This will include periods identified as such in the subjects' sleep logs, in addition to actigraphy data in which no activity is present for more than 30 consecutive minutes, and days that contain more than 10% of missing data, and data sets with fewer than 2 days of valid data. The balanced assignment of the two intervention sequences is designed to minimize any adverse impact with respect to period and carryover effects, as is use of a washout period in the experimental design. However, we can explicitly test for a period effect by including a dummy variable in the linear mixed model (with period one as the reference). We will also adjust for covariates that may be found to be associated with night-time sleep, such as gender, age, cognitive status, functional status, baseline sleep disturbance and sedative medication load; however, because of the crossover

nature of the study, in which participants serve as their own controls, it is not expected that covariate adjustment will markedly alter estimates of treatment effect.

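### Read literally, the SAP's 30-minute inactivity rule deletes motionless sleep with the monitor on from four primary actigraphy outcomes; the documents do not let the size be determined

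*SAP*

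**What the plan says.** The cleaning step is in the SAP, Statistical Analysis. Its purpose is that "actigraph data recorded while the monitor is not worn will be identified and removed from the analyses". The criteria follow: "This will include periods identified as such in the subjects' sleep logs, in addition to" the next items, "actigraphy data in which no activity is present for more than 30 consecutive minutes, and days that contain more than 10% of missing data". A further exclusion is "data sets with fewer than 2 days of valid data".

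The primary sleep measures from the same recordings are "minutes of sleep, sleep onset latency, sleep efficiency, and circadian rhythmicity from actigraphy data". The remaining two, PSQI and MALSQ, are questionnaires. Recording covers a fourteen-day baseline, "plus two seven-day intervention data collection periods for each treatment condition". On unequal data the SAP says: "These analyses allow for different numbers of observations for different participants".

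The Protocol's Study Protocol section does not mention actigraphy cleaning. Neither document gives the device, its epoch length, the count that defines zero activity, how often participants move in their sleep, what a day is, or whether minutes removed by the inactivity rule count towards the 10% limit.

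**The concern.** The log criterion and the inactivity criterion are joined additively. The second therefore needs no confirmation from the log, and it is not limited to waking hours or to time out of bed. In a sleep trial, stillness is much of the signal. A rule that treats stillness as evidence that the monitor was off selectively removes the stillest sleep.

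Three things follow for the analysis.

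- If deleted minutes are not scored as sleep, deleting runs lowers minutes of sleep. If whole days are also lost, the direction is not fixed: should the dropped still nights be shorter than the retained ones, the mean can rise.
- The effect on sleep efficiency depends on whether deleted minutes also leave the denominator. The direction for onset latency and rhythmicity cannot be worked out from the documents.
- The deletion depends on the outcome. The mixed model accommodates unequal numbers of observations, but that does not correct for observations removed because the participant was still.

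Two analysts following the same text could also reach different primary results, one applying the rule to all 24 hours and the other to waking hours only.

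**Working it through.** The plan gives no figure to reproduce, so the check is a reading of the rule, the arithmetic of its limits, and an illustration with assumed inputs.

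**1. Does worn sleep meet the rule?** A run of 31 minutes without movement exceeds 30. No other condition is stated, so it does.

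**2. The day limit.** Assume a day is 24 hours and removed minutes count as missing. The limit is 0.10 × 1440 = 144 min. Four 31-minute runs (124 min) stay within it; five (155 min) discard the day. If a day meant a night window of 420 to 540 min, the limit would be 42 to 54 min, and two such runs (62 min) would exceed it.

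**3. Sleep efficiency.** Assume 360 min asleep in 480 min in bed: 360/480 = 75.0%. Deleting one 31-minute run gives 329/480 = 68.5% if time in bed is kept whole, or 329/449 = 73.3% if it is cut too.

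**4. Minutes deleted per night (illustration).** Assume exponential gaps between movements with mean m minutes, and T minutes of sleep. With x = 30/m, the expected loss to runs over 30 minutes is D(T, m) = e^(−x) × [T(1 + x) − 30x]. For T = 420:

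- m = 3: 0.0000454 × (4620 − 300) = 0.2 min
- m = 5: 0.002479 × (2940 − 180) = 6.8 min
- m = 10: 0.04979 × (1680 − 90) = 79.2 min
- m = 15: 0.13534 × (1260 − 60) = 162.4 min

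Adding four awakenings per night (simulated, 200,000 nights per condition) gives about 0.2, 5, 63 and 133 min.

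**5. Contrast with equal stillness.** Assume 420 min of sleep on active and 390 on control, a true difference of +30. With run deletion only, the estimate is 30 − [D(420, m) − D(390, m)] = 30 × [1 − (1 + x)e^(−x)]:

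- m = 3: 30 × (1 − 0.0005) = +30.0
- m = 5: 30 × (1 − 0.0174) = +29.5
- m = 10: 30 × (1 − 0.1991) = +24.0
- m = 15: 30 × (1 − 0.4060) = +17.8

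Four awakenings give nearly the same values. The longer sleep simply has more minutes to lose. If removed minutes also count towards the 144-minute limit, the simulated estimate is about +25 to +30, because the most heavily cut days drop out. The cost is then lost days: at 420 min, 10.3% of days at m = 10, or 0.103 × 14 = 1.4 of the 14 planned per condition (0.7 with four awakenings).

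**6. Contrast with unequal stillness.** Control m = 5, active m = 7. Active loss: 0.013764 × (2220 − 128.6) = 28.8 min. Control loss: 0.002479 × (2730 − 180) = 6.3 min. Estimate: (420 − 28.8) − (390 − 6.3) = +7.5 with run deletion only, or about +12 with four awakenings. With both rules it is about +8 and +12.

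With the stiller condition reversed, control m = 12 and active m = 10, the control loss is 0.08208 × (1365 − 75) = 105.9 min. The estimate is (420 − 79.2) − (390 − 105.9) = +56.7 with run deletion only, and about +45 with both rules.

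**The case against.** The strongest reply is that the criterion sits under a sentence about non-wear. It can be read as a way of recognising an unworn monitor, and sensible analysts would apply it to waking hours. That reading fits the stated purpose, and it is why the point is confined to the rule as written. But the text does not limit the rule in that way and gives no means of telling still sleep from an absent monitor. If waking hours were meant, a clause settles it.

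A second reply is that nothing in the documents shows any loss. This stands as regards size. At a mean gap of 3 minutes the loss is trivial, and the larger figures need gaps of about 10 to 15 minutes or a difference in stillness between conditions. The gaps are assumed, the modelled awakenings have no duration, and night length does not vary.

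A third is that a counterbalanced crossover with the same cleaning in both conditions should cancel the error. It limits differential bias but does not remove it: under run deletion alone, equal stillness still attenuates the difference, as step 5 shows.

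A reader might go further and infer that the actigraphy results are shown to be wrong, or that the rule works against the blue-light mask. The documents support neither. They do not say how still participants are, or whether one mask makes sleep stiller.

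**Conclusion.** The point holds as a defect in a stated rule. Followed literally, the rule deletes motionless worn sleep from four of the six listed primary sleep measures; PSQI and MALSQ are untouched. It should be fixed, with medium confidence in how much it matters.

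The downward bias in minutes of sleep assumes that deleted minutes are not scored as sleep and that only runs, not whole days, are removed. The treatment contrast can be distorted with equal stillness and more so with unequal stillness. Where stillness differs, the illustrations move against the stiller condition. The size ranges from negligible to large according to movement frequency, which is not given. Every minute figure rests on assumed exponential gaps and fixed sleep lengths, and every both-rules figure also on a 24-hour day with removed minutes counted as missing. They show what the wording permits, not what happened in this trial.

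**What to change.** Apply the 30-minute rule only outside the in-bed interval. Take that interval from the sleep logs if they record bed and rise times; the SAP says only that they identify non-wear, so this must be checked. Otherwise use the rest interval on which sleep is scored. Inside it, remove data only where the log shows non-wear or, if the device records one, an off-wrist signal does.

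Apply the 10% limit after this correction. State what a day is and whether removed minutes count as missing. Report excluded minutes and days by condition, so that unequal loss is visible. Optionally, pre-specify a sensitivity analysis that leaves out nights with very long in-bed runs of zero activity; its cut-off is a judgement.

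The cost is a short change of SAP wording and a re-run of the cleaning, provided an in-bed interval is available. The downside is that unlogged removal at night may be scored as sleep. Assuming 60 min on 5% of nights (range 2% to 10%), mean sleep rises by 60 × 0.05 = 3.0 min (60 × 0.02 = 1.2 to 60 × 0.10 = 6.0). This cancels in the contrast if it is equally common in both conditions.

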## **Study Protocol**

The study will be a randomized trial in 50 community-dwelling older adults with early awakening insomnia who live at home, using a within-subject crossover design. The control condition will be a red light mask; the intervention will be a blue light mask (individualized to the patient's light exposure and circadian rhythm). Subjects will use each condition for eight weeks, with the intervention order counterbalanced across subjects, a two-week baseline observation period, and a two-week washout period between the two study conditions. Outcomes will be assessed at baseline and 8 weeks for all measures except for (a) side effects, adverse effects, and protocol deviations, which will be monitored weekly, and (b) clinical eye examinations, which will be conducted at baseline and at the end of each study condition.

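### The SAP puts actigraphy baseline days in the dependent variable without giving them a level in the model, and leaves the period term optional

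*SAP*

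**What the plan says.** In the SAP's Statistical Analysis section, the efficacy model has a random effect for participant and "a fixed effect for treatment (i.e. a dummy variable for the experimental condition, with the control condition as the reference category". The Protocol (Study Protocol) defines the reference: "The control condition will be a red light mask".

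For actigraphy, the measures forming the dependent variable are described as "a fourteen-day baseline, plus two seven-day intervention data collection periods for each treatment condition". For the questionnaires, the dependent variable is "one of the survey sleep measures (two observations per treatment condition) as the dependent variable". The Protocol puts most assessments at baseline and at 8 weeks, so it is unclear whether one of the two survey values in a condition precedes treatment.

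Period is not in the sentence that defines the model. After relying on balanced sequences and the washout, the SAP adds that "we can explicitly test for a period effect by including a dummy variable in the linear mixed model (with period one as the reference". The covariate sentence is firmer: "We will also adjust for covariates that may be found to be associated with night-time sleep". The SAP also says "These analyses allow for different numbers of observations for different participants", and its cleaning rules remove, among other data, "days that contain more than 10% of missing data".

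**The concern.** Baseline days are neither blue nor red, and they come before period one. A 0/1 treatment dummy and a 0/1 period dummy have no level for them, and the SAP states no separate indicator and no exclusion. An analyst who applies the treatment dummy literally (experimental = 1, everything else = 0) merges unmasked nights with red-mask nights. The coefficient is then no longer blue minus red. Any change from baseline that both masks share, for example from wearing a mask, being in a study or the passage of time, enters the treatment estimate. Counterbalancing and washout do not protect against this, because the distortion does not depend on sequence.

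The period point is smaller. If period may be tested and then kept or dropped, two estimates are available, and they differ once the sequences contribute unequal data.

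**Working it through.** The documents give no effect size, SD, dropout rate or power calculation, so there is no planned figure to reproduce. The checks below use generalised least squares with a random participant effect.

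**Inputs.** 50 participants and counterbalanced order (Protocol), taken as 25 per sequence. Actigraphy by the night: b = 14 baseline nights and m = 2 × 7 = 14 nights per condition (SAP). Actigraphy by data collection period: b = 1 and m = 2. Surveys: m = 2 per condition (SAP). All other values are assumptions and are marked as such.

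**1. Baseline coded 0 on the treatment dummy, complete data.** Each person has the same counts, so the coefficient is the blue mean minus the mean of all other observations. For a change c common to both masks and no blue–red difference:

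- Treatment dummy only: bias = c·b/(b + m).
- Period dummy added, baseline also 0: bias = c·b/(1.5b + m).

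| Unit | b, m | Without period | With period |
|---|---|---|---|
| Night | 14, 14 | 14/28 = 50% | 14/35 = 40% |
| Night, 10 valid baseline nights | 10, 14 | 10/24 = 42% | 10/29 = 34% |
| Night, 7 valid baseline nights | 7, 14 | 7/21 = 33% | 7/24.5 = 29% |
| Data collection period | 1, 2 | 1/3 = 33% | 1/3.5 = 29% |

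These fractions need no assumed SD and were the same at intraclass correlations of 0.1, 0.5 and 0.9. With period omitted, half as much of a period shift also enters: ½·b/(b + m), or 25% at 14+14+14 nights. With baseline in its own level, or left out, both biases are 0. Adjusting for a person's baseline mean does not repair the zero coding: it is constant within a person, and with complete data the treatment estimate does not move.

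**2. What this could do to a test (assumed values).** In units of the within-person night SD, with N = b + 2m = 42 and independent nights:

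- Treatment only: SE = 1/√(50·m(b + m)/N) = 1/√(50 × 9.333) = 0.0463.
- Treatment and period: SE = 1/√(50 × 8.75) = 0.0478.
- On-treatment only: SE = 1/√(50·m/2) = 1/√350 = 0.0535.

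For an assumed common change of 0.2 SD and no true difference, z = 0.10/0.0463 = 2.16 and 0.08/0.0478 = 1.67. The two-sided 5% test then rejects about 58% and 39% of the time. For 0.1 SD the figures are 19% and 13%. With one value per data collection period and the same 0.2 SD change, simulation gives about 29% and 22–23%. Without the zero coding the rate returns to about 5%, but only if nights are independent given the participant.

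**3. Period omitted, on-treatment data, complete 25:25.** There is no bias. The SE is multiplied by √(1 + k²/(2m − 1)), where k is the period shift in SDs of the within-person difference (assumed 0.5 or 1):

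- m = 14: √(1 + 0.25/27) = 1.005; √(1 + 1/27) = 1.018.
- m = 2 (surveys): 1.041; 1.155.
- m = 1 (if one of the two survey values precedes treatment): 1.118; 1.414.

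**4. Period omitted, one sequence loses d of 25 second periods (assumed).** If only within-person information counted, the bias would be d/(50 − d) of the period shift: 2/48 = 4.2%, 4/46 = 8.7%, 6/44 = 13.6%, 8/42 = 19.0%. Generalised least squares also uses between-person information and gives slightly less:

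| d | 14 nights | Two values |
|---|---|---|
| 2 | 4% | 3–4% |
| 4 | 8–9% | 6–9% |
| 6 | 13–14% | 10–13% |
| 8 | 18–19% | 14–19% |

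The ranges cover intraclass correlations of 0.3 to 0.9. The bias is 0 with a period term, and 0 if both sequences lose equally.

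**The case against.** The strongest reply is that the SAP never says baseline is coded as control. It names the control condition as the reference, and the Protocol defines control as the red mask, so pooling unmasked nights with red-mask nights would contradict the definition. Baseline may be meant only for the covariate on baseline sleep disturbance. This stands against inferring that the trial's actigraphy results will be biased towards blue. It does not settle where baseline belongs, because the SAP lists those days with the dependent variable and gives them no code.

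A reader might also take 50% leakage and 58% false positives as the size of the problem. The documents do not support that. They do not say that the night is the unit; dropping data sets with fewer than 2 valid days is compatible with one summary per data collection period, where leakage is 33% or 29%. The false-positive rates rest on an assumed common change and on independent nights. The sign is open too: a shared worsening would count against a measure on which blue does better.

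On period, the SAP names the dummy and its reference level and gives a reason for relying on balance. A reader might infer that omitting period biases the comparison. With complete balanced on-treatment data it does not, and at 14 nights the loss of precision is slight. One-sided dropout is an assumption; the documents report none. What remains is that the SAP expects unequal numbers of observations and does not commit to the term that protects against them.

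**Conclusion.** The concern holds as a gap in specification with a conditional bias. The primary model has no valid place for the baseline days it includes. Under the zero coding, 29–50% of a shared change from baseline moves into the blue–red contrast, depending on the unit and on whether period is included, and this happens with complete data. If there is no shared change and no period shift, or if another coding is used, there is no such bias.

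The optional period term is the lesser part: no bias under balance, 0.5–2% in SE at 14 nights, 4–15% at two survey values, and about 3–19% of the period shift under the assumed one-sided losses. Survey outcomes share the baseline problem only if one of their two values per condition precedes treatment, which the two documents leave unclear.

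The change should be made because it is cheap and removes both ambiguities. Confidence is medium, since the size depends on a coding the SAP does not state.

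**What to change.** Add to the SAP's Statistical Analysis section:

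> The primary model for every outcome includes fixed effects for treatment and period, whatever the result of any test of period. Only on-treatment observations form the dependent variable; baseline or other pre-treatment values, actigraphy or survey, are never coded as control or as period one and enter only as a covariate.

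The SAP should also say whether the actigraphy unit is the night or a summary per data collection period, and which two survey values per condition are meant. If nights are the unit, it should state how correlation within a period is handled: with an assumed person-by-phase SD of 0.4 night SD, a random intercept alone gave about 25–28% false positives even with baseline handled correctly.

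The cost is this wording and one degree of freedom for period. For nightly actigraphy the SE is 0.0535/0.0478 = 1.12 to 0.0535/0.0463 = 1.15 times that under the zero coding. That extra precision came from borrowing untreated nights as control nights. No change to design or conduct is needed.
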